10.2 Sample Size and Accrual

15 to 21 patients may be recruited.

10.3 Evaluable Cohort and Subject Replacement

A subject will be considered evaluable for assessment of DLT if the subject receives at least 7 days of DMF and completes the safety follow-up through the DLT evaluation period, or the subject experiences a DLT at any time during the DLT evaluation period. Any non-evaluable subject will be replaced in the same dose cohort to complete the number of evaluable subjects for the MTD analysis.

Any subject who receives at least one dose of DMF is evaluable for safety. The safety population will be used to evaluate baseline characteristics as well as all descriptive endpoints for safety.

All patients who undergo at least one dose of the study treatment will be included in the efficacy analysis. If the response for a patient cannot be assessed (for example, a patient dies early) prior to 2 months assessments, it will be considered to be an event that does not favor the study therapy (e.g., non-response).

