5.0 TREATMENT PLAN

5.1 Treatment Dosage and Administration

For Dose Level 1, DMF (Tecfidera formulation) will be administered at a dose of 120 mg PO BID (approximately 12 hours apart) for 2 x 28 day cycles.

For Dose Level 2, DMF will be administered at the currently used dose for patients with multiple sclerosis: 120 mg PO BID for 1 week, then escalate to the dose of 240mg PO BID for the remainder of 2 x 28 day cycles. The 1 week lead-in at 120 mg is to assist in toleration and initial side effects and is as per the standard prescribing information.

For Dose Level 3, DMF will be administered at the currently used dose for patients with multiple sclerosis: 120 mg PO BID for 1 week, then escalate to the dose of 360mg PO BID for the remainder of 2 x 28 day cycles.

The medication can be taken with or without food. Capsules should not be crushed or chewed. Capsules will be self-administered on an outpatient basis. On days in which patients are scheduled for assessment, capsules will be taken in clinic. Missed or vomited doses will be skipped. Patients are assessed for safety and tolerability on Day 8, Day 1 of each subsequent cycle, and 28 days and 56 days following the last dose of DMF.

Dose Level	DMF dose (all cohorts start at 120 mg PO BID dose for 1 week, then increase to the assigned dose)
1	120 mg PO BID
2	240 mg PO BID
3	360 mg PO BID

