5.2 Definition of Dose-Limiting Toxicity

Dose Limiting Toxicity (DLT) is defined as any of the following adverse events that are considered by the investigator to be possibly, probably or definitely related to DMF within the DLT evaluation timeframe.

- Non-hematologic adverse events: grade 3 (CTCAE 4) or higher, lasting more than 7 days despite appropriate medical management.
- Hematologic adverse events: grade 3 (iwCLL 2008) or higher, lasting more than 7 days despite appropriate medical management, with the exception of: any grade lymphopenia ; or any grade lymphocytosis.
- Grade 4 non-hematologic (CTCAE 4) of any duration
- Grade 4 hematologic (iwCLL 2008) of any duration.
- Any clinically significant toxicity that precludes administration of the next scheduled dose beyond 14 days

Replacement patients may be enrolled for patients who withdraw from investigational treatment for a reason that is definitely unrelated to toxicity of the study agent or disease progression (e.g. patient preference, loss to follow-up). Replacement patients will ensure enough patients are enrolled to evaluate the primary endpoint.

The DLT evaluation timeframe is from the first dose of DMF until day 56 of the trial.

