5.7 Toxicities and Dosing Delays/Dose Modifications

Any patient who receives treatment on this protocol will be evaluable for toxicity. Each patient will be assessed for the development of toxicity according to the NCI Common Toxicity Criteria for Adverse Events (CTCAE), version 4.03 for non-hematologic adverse events, and 2008 international working group criteria (iwCLL, Hallek et al, appendix B) for hematologic adverse events. Dose adjustments should be made according to the system showing the greatest degree of toxicity. Patients are assessed for safety and tolerability on Day 8, Day 28, and Day 42 after starting DMF.

Toxicity – NCI CTCAE Grade (Hematologic- iwCLL)	Occurrence	Dose Modification
Non-hematologic		
Grade ≥ 3	1st	Withhold study treatment until resolved to Grade ≤ 1.

		Resume study treatment at the next lower dose level.
	Repeat	Discontinue therapy.
Hematologic*		
Grade \geq 3	1st	Withhold study treatment until resolved to ANC \geq 1000/mm ³ , hemoglobin is \geq 8 gm/dL, and platelet count \geq 50,000/mm ³ . Resume study treatment at same dose.
	2nd	Withhold study treatment until resolved to ANC \geq 1000/mm ³ , hemoglobin is \geq 8 gm/dL, and platelet count \geq 50,000/mm ³ . Resume study treatment at the next lower dose level.
	3rd	Permanently discontinue study treatment.
*Dose adjustments or dose holds for hematologic toxicity will apply even if the baseline values are lower than these thresholds due to heavily infiltrated marrow. In those cases, growth factors and/or blood product transfusion may be administered prior to continuing with DMF.		

Notes:

1. If any of the above are noted, the patient will be re-assessed within 7 days by the treating physician or investigator. Isolated laboratory abnormalities may be re-evaluated by laboratory draw only, or based on physician or investigator discretion.
2. DMF can be delayed for a maximum of 14 days; if not restarted in that time-span, study treatment will be permanently discontinued.
3. If dose is decreased for toxicity, dose re-escalation is not planned.
4. For invasive procedures, not including biopsies or venous catheter placement: withhold study treatment for 1 week prior to procedure, and at least 1 week following surgery until satisfactory wound healing has been achieved.

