6.3.1.1 Review concomitant medications

6.3.1.2 Physical exam including vital signs (temperature, pulse, respirations, blood pressure), weight; and including bidimensional measurement of palpable lymph nodes, spleen size (below the costal margin), and liver size (craniocaudal size at the right midclavicular line).

6.3.1.3 Performance status using ECOG grading scale.

6.3.1.4 Adverse event assessment: See Section 9 for adverse Event monitoring and reporting.

6.3.1.5 Hematology: hemoglobin (Hgb), platelets, total white blood cell count (WBC), and differential.

6.3.1.6 Serum chemistries: Comprehensive metabolic panel (CMP) to include: albumin, alkaline phosphatase, ALT/SGPT, AST/SGOT, BUN, creatinine,

electrolytes (sodium, potassium, calcium, chloride, bicarbonate), glucose, and total bilirubin. Also: LDH, uric acid, phosphorous

6.3.1.7 Blood draw for correlative studies: Up to 20 mL in anti-coagulated (ACD) tubes.

6.3.1.8 Dispense DMF 120 mg PO BID x 7 day supply.

6.4.1.9 6-8 hours after DMF dosing: Repeat Hematology and serum chemistries, in addition to LDH, uric acid, and phosphorous. Blood draw for correlative studies: Up to 10 mL in anti-coagulated (ACD) tubes.

6.3.2 Visit 3: Day 8

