6.3.2.8 Dispense DMF at assigned dose x 21 day supply

6.3.3 Visits 4: Day 1 of cycles 2

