10.1.1 Statistical Design

A standard 3+3 dose escalation design will be used. There are two test dose levels with a potential de-escalation dose. A minimum of three subjects will be treated at each dose level. All three subjects in a cohort will be evaluated for DLT in the defined DLT evaluation period (within 56 days of starting study treatment) before enrollment of subjects at the next dose level may begin. For all dose levels, if no DLTs are observed during the evaluation period among the three treated patients, escalation to the next dose level may begin. If a DLT is observed in one of the first three subjects in the cohort, the cohort will be expanded to six subjects. If zero or one of six subjects in the cohort experiences a DLT within the evaluation period, escalation to the next dose level will occur. If a DLT is seen in two or more subjects in a cohort, escalation will be stopped and the Maximum Tolerated Dose (MTD) will be considered to have been exceeded. The next lower dose will be considered as MTD if six patients have already been treated at that dose. Otherwise if only three patients have been treated at the next lower dose, then an additional three patients should be enrolled at the next lower dose level for a total of six

patients. If zero or one has DLTs among the 6 patients, then this dose is declared as MTD. Otherwise, there is further de-escalation according to the same scheme. As a result, the MTD is the highest dose where at most one-sixth of the patients developed DLT. If MTD is not reached, the higher dose will be selected. As with MTD, another 3 subjects will be treated at this dose if only 3 subjects have been treated.

1 additional cohort with 3 patients will be recruited at the selected dose to further evaluate the safety. The sample size of 9 subjects is considered to be sufficient to support preliminary tolerability, safety, and DLTs based on the established safety profile of this compound.

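### For a patient without a DLT, Section 10.3 asks for 7 days of DMF at no stated dose plus follow-up to Day 56; at Levels 2 and 3 the 120 mg lead-in alone can supply those 7 days

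*Combined protocol and SAP*

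**What the plan says.** Section 10.3 gives two ways to be evaluable for DLT. One is to have a DLT at any time in the evaluation period. The other, for everyone else, applies "if the subject receives at least 7 days of DMF and completes the safety follow-up through the DLT evaluation period". Only subjects who meet neither must be replaced under that section. Section 5.2 sets the period as first dose to Day 56.

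The dose table in Section 5.1 states that "all cohorts start at 120 mg PO BID dose for 1 week, then increase to the assigned dose". The visit schedule agrees. On Day 1 (Section 6.3.1) the instruction is "Dispense DMF 120 mg PO BID x 7 day supply"; on Day 8 (Section 6.3.2) it is "Dispense DMF at assigned dose x 21 day supply"; a further 28-day supply follows at Cycle 2 Day 1 (Section 6.3.3).

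The escalation rules in Section 10.1.1 are worded by treatment at a dose: "A minimum of three subjects will be treated at each dose level", and the next lower dose becomes the MTD "if six patients have already been treated at that dose". The primary analysis in Section 10.4 likewise uses patients treated at the selected dose. Neither section defines what being treated at a dose requires.

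**The concern.** The 7-day minimum has the same length as the lead-in. At Level 1 this does no harm, because the lead-in dose is the assigned dose. At Levels 2 and 3 a patient can meet the minimum without taking one capsule at the dose being tested, and if follow-up reaches Day 56 that patient enters the cohort count as a non-DLT.

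A 3+3 decision turns on single patients: one DLT in six clears a level and two stop it. A non-DLT place filled by someone who never took the assigned dose makes the level easier to clear than its true DLT rate warrants. The same count feeds the MTD and the primary DLT rate, so the error would run through the primary endpoint in the less cautious direction.

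**Working it through.** **Exposure.** Two 28-day cycles give 2 × 28 = 56 days, which reproduces the DLT period in Section 5.2. Planned days at the assigned dose at Levels 2 and 3 are 56 − 7 = 49, and dispensing agrees (21 + 28 = 49), or 98 doses at two a day. The fewest assigned-dose days compatible with the 7-day condition are 7 − 7 = 0. In total dose, the lead-in is 7 × 240 mg = 1,680 mg. That is 6.7% of the Level 2 plan (1,680 + 49 × 480 = 25,200 mg) and 4.5% of the Level 3 plan (1,680 + 49 × 720 = 36,960 mg).

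**How it could arise.**

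1. *Early stop.* A patient stops after Day 7 without a DLT and stays in follow-up, which Section 6.5.2 permits. Section 10.4 and the schedule in 6.1 run toxicity assessment to 56 days after the last dose: 7 + 56 = Day 63, so Day 56 is covered. Section 8.1 ends adverse event monitoring 28 days after the last dose: 7 + 28 = Day 35. If 8.1 governs, the follow-up condition fails and 10.3 replaces the patient.
2. *Dose reduction.* Under Section 5.2 a non-hematologic event is a DLT if it is "grade 3 (CTCAE 4) or higher, lasting more than 7 days despite appropriate medical management". A Grade 3 lead-in event of 7 days or less does not meet that item. For a first such event Section 5.7 withholds treatment and then says "Resume study treatment at the next lower dose level", with no re-escalation planned. Read from the assigned level, a Level 2 patient stays on 120 mg BID and a Level 3 patient resumes at the Level 2 dose, each with 0 days at the assigned dose. Read from the 120 mg BID being taken, the dose table has no lower level and this route does not operate as described.

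**Effect on clearing a level.** Let p be the true DLT rate at the assigned dose (assumed; the documents give none). Suppose one counted patient has no exposure to that dose and, as an upper bound, no DLT risk.

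- No such patient: (1−p)³ + 3p(1−p)⁵
- One among the first three: (1−p)² + 2p(1−p)⁴
- One among the second three: (1−p)³ + 3p(1−p)⁴

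| p | None | In first three | In second three |
|---|---|---|---|
| 0.10 | 0.906 | 0.941 | 0.926 |
| 0.20 | 0.709 | 0.804 | 0.758 |
| 0.30 | 0.494 | 0.634 | 0.559 |
| 0.40 | 0.309 | 0.464 | 0.372 |

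At p = 0.30, for example: 0.343 + 0.9 × 0.16807 = 0.494; 0.49 + 0.6 × 0.2401 = 0.634; 0.343 + 0.9 × 0.2401 = 0.559. From unrounded values the increases are 0.035, 0.095, 0.140 and 0.154 in the first three, and 0.020, 0.049, 0.065 and 0.062 in the second three.

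**MTD confirmation.** After 0 of 3, three more patients are added and at most one DLT is allowed: (1−p)³ + 3p(1−p)² = 0.972, 0.896, 0.784, 0.648. With one unexposed patient among the added three: (1−p)² + 2p(1−p) = 0.990, 0.960, 0.910, 0.840.

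**Opposite scoring.** If the patient, among the first three, is counted as a DLT, the chance of clearing is (1−p)⁵ = 0.590, 0.328, 0.168, 0.078. How such patients are scored therefore matters in both directions.

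**The case against.** The case on the other side is substantial, and much of it limits the point.

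- A reader might infer that 7 days of DMF is enough by itself. It is not: 10.3 joins exposure to follow-up through Day 56, and under the 28-day window of 8.1 a Day 7 stopper would not qualify.
- A reader might infer that patients who cannot tolerate the lead-in are counted as clean. For the clearest cases the documents say otherwise. Section 5.2 makes any related, clinically significant toxicity that blocks dosing for more than 14 days a DLT, and Grade 4 events count at any duration. The early-stop route is left mainly with preference, progression, intercurrent illness, or toxicity judged unrelated or not clinically significant. Section 5.9 also ends follow-up at progression, so some of those patients may not reach Day 56.
- Section 5.2 lets the investigator replace patients whose withdrawal clearly had nothing to do with toxicity or progression. This helps, but it is optional and does not say that the patient stops being evaluable under 10.3.
- It is tempting to say that such a patient tells us nothing about the assigned dose. That goes too far for the dose-reduction route: a Grade 3 event at 120 mg BID bears on a higher dose, and the patient resumes DMF and remains at risk. The zero-risk figures are an upper bound there.
- The wording of 10.1.1 and 10.4 suggests that exposure at the assigned dose is intended. That stands as evidence of intent, but the only operative definition, and the one that drives replacement, is in 10.3.

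None of this supplies the missing requirement. No section sets a minimum exposure at the assigned dose.

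**Conclusion.** The evaluability rule in 10.3 is wrong as written for Levels 2 and 3. Its exposure condition can be met with 0 of 49 assigned-dose days. That follows from the text and schedule and needs no assumption.

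Whether a given patient is then counted depends on unresolved conflicts: the 28-day window against the 56-day window for early stops, and the reference level in 5.7 for dose reductions. The documents give no discontinuation or reduction rate, so frequency cannot be estimated and nothing here shows that a level would in fact be cleared wrongly.

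Given one such patient and zero DLT risk, clearance rises by about 0.02 to 0.04 at an assumed 10% DLT rate. At 30 to 40% it rises by about 0.14 to 0.15 when the patient is in the first three, but only about 0.06 in the second three. The larger figure should not be quoted alone. The point is a should-fix because the correction is cheap and the primary endpoint depends on the count.

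**What to change.** In 10.3, for a subject without a DLT at Levels 2 and 3, count the minimum exposure at the cohort's assigned dose within the 56-day window. The sponsor should set that minimum in advance, for instance as a share of the 98 planned doses. State that lead-in exposure alone does not make a subject an evaluable non-DLT at that level. Any subject with a DLT stays evaluable.

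Replace subjects who fall short because they stopped for reasons clearly unrelated to toxicity or progression, as 5.2 already allows. Do not automatically replace those reduced or stopped for sub-DLT toxicity before reaching the assigned dose. Removing them would conflict with 5.2, would be an informative exclusion, and could itself make a level easier to clear. Instead, reconcile 10.3 with 5.2 on how they count, list them separately, and report the DLT rate with them scored as DLTs and as non-DLTs.

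Use one evaluable set for the escalation decision (10.1.1) and the primary DLT rate (10.4). Reconcile optional replacement in 5.2 with mandatory replacement in 10.3, the adverse event windows of 8.1 and 10.4, and the level from which 5.7 counts downward. No dose or clinical rule is proposed.

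The cost is a wording amendment, possibly one or two replacement patients, and a longer cohort, since each replacement must be observed for a further 56 days.

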10.4 Data Analyses Plans

Primary Analysis

The rate of DLTs will be estimated along with its exact 95% confidence interval using the patients treated at the selected dose in Phase I.

Secondary analyses

The adverse events from the treatment beginning to 56 days after treatment completion or study discontinuation will be recorded for all patients. Incidence of adverse events will be summarized by event type, grade and relatedness, separately for the two dose levels.

The proportion of patients that received the selected dose and are able to complete 2 months of therapy without intolerance or disease progression will be reported. The reason for patient discontinuing treatment early will be recorded.

The objective response rate (including partial response, complete response, or nodular complete response) based on iwCLL will be estimated along with its exact 95% confidence interval.

If follow-up is available, median progression-free survival and overall survival will be estimated using the Kaplan-Meier method.

The expressions of LEF1, c-myc, Wnt pathway, STAT pathway, and STAT1 phosphorylation will be measured over time. The trajectories will be showed by graphs. We will test if the average level of these measurements throughout the treatment is significantly changed from the pre-treatment level by a paired t-test at 5% significance level. We will use the methods of Smyth (2005) to fit linear models to assess differential expression between pre- and post-treatment measurements. As we plan to conduct a large number of hypothesis tests within the gene expression outcome, we will use the Benjamini-Hochberg method to control the false discovery rate (FDR), setting it to 5%.

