3.2 Secondary Endpoints

- 3.2.1** Treatment-emergent adverse events, including infections (description, timing, grade [CTCAE v4.03], severity, seriousness, and relatedness)
- 3.2.2** Percent of patients who achieve an objective response (partial response, complete response, or nodular complete response) by international working group in CLL guidelines (iwCLL).
- 3.2.3** Pharmacodynamic activity including measurement of expression of LEF1, c-myc; Wnt and STAT pathway expression; and STAT1 phosphorylation.

3.2.4 Percent of patients able to complete 2 months of therapy without intolerance or disease progression.

3.2.5 Progression free survival, also based on the iwCLL definition of disease progression.

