5.9 Duration of Follow Up

Patients will be followed for 1 year after removal from treatment or until disease progression, initiation of subsequent CLL therapy, or death, whichever occurs first. Patients removed from treatment for unacceptable adverse events will be followed until resolution or stabilization of the adverse event.

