6.0 STUDY PROCEDURES

6.1 Schedule of Events

	Screening	Cycle 1 Day 1 (C1D1)	C1 D8	C2, D1	Up to 28 days after last DMF dose	56 days after last DMF dose	Follow-up (q 56 days until 1 year)
Visit Number	1	2	3	4	5	6	7-
Window	+/- 3 days		+/- 2 d	+/-7 d	+/-7 d	+/-7 d	+/-14 d
Informed Consent	X						
Serum Pregnancy test	X						
History and PE	X	X	X	X	X	X	X
Performance Status	X	X		X	X	X	X
Toxicity (include DLT) Evaluations		X	X	X	X	X	
Tumor Measurements by physical examination	X	X	X	X	X	X	X
CBC with differential	X	X (x2 – pre and post dose)		X	X	X	X
Comprehensive Metabolic Panel *	X	X (x2 – pre and post dose)	X	X	X	X	X
LDH, uric acid, phos		X (x2 – pre and post dose)					
Correlative laboratory collection **	X	X (x2 – pre and post dose)	X	X	X	X	
CT or MRI scan with contrast of chest, abdomen, pelvis					X		
Bone marrow biopsy and aspirate ***					X (if clinical response and imaging is consistent with CR)		

* Comprehensive metabolic panel (CMP) to include: albumin, alkaline phosphatase, ALT/SGPT, AST/SGOT, total bilirubin, electrolytes (sodium, potassium, calcium, chloride, bicarbonate), BUN, creatinine, glucose.

** Up to 30 mL in anti-coagulated (ACD) tubes for screening visit; up to 20 mL in anticoagulated (ACD) tubes for subsequent visits. To be drawn prior to DMF dosing.

*** With flow cytometric and immunohistochemical evaluation of CLL cell infiltrate; and chromosome and FISH analysis (including 11q, 12p, 13q, and 17p).

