6.3.5 Visit 6: 56 days after the last dose of DMF

6.3.5.1 Review concomitant medications

6.3.5.2 Physical exam including vital signs (temperature, pulse, respirations, blood pressure), weight; and including bidimensional measurement of palpable lymph nodes, spleen size (below the costal margin), and liver size (craniocaudal size at the right midclavicular line).

6.3.5.3 Performance status using ECOG grading scale.

6.3.5.4 Adverse event assessment: See Section 9 for adverse Event monitoring and reporting.

6.3.5.5 Hematology: hemoglobin (Hgb), platelets, total white blood cell count (WBC), and differential.

6.3.5.6 Serum chemistries: Comprehensive metabolic panel (CMP) to include: albumin, alkaline phosphatase, ALT/SGPT, AST/SGOT, BUN, creatinine,

electrolytes (sodium, potassium, calcium, chloride, bicarbonate), glucose, and total bilirubin.

6.3.5.7 Blood draw for correlative studies: Up to 20 mL in anticoagulated tubes.

6.3.6 Visits 7-10: Every 56 days to one year (typically month 6, 8, 10, 12)

Patients will be followed every 56 days after completion of (or early withdrawal from) study treatment until subsequent CLL therapy, death, or discontinuation of trial participation. Follow-up will consist of survival contacts via medical record review, telephone call, or review of the Social Security Index.

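### Sections 5.9, 6.1 and 6.3.6 conflict on follow-up; if 6.3.6 is followed, no examination or blood count that can show progression is mandated after nominal Day 112, which weakens the planned PFS estimate

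*Combined protocol and SAP*

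**What the plan says.** Section 3.2 lists as a secondary endpoint "Progression free survival, also based on the iwCLL definition of disease progression", and section 2.0 makes durability of clinical activity a secondary objective. Section 7.1.1 measures PFS from the start of treatment to objective progression or death. Section 10.4 plans: "If follow-up is available, median progression-free survival and overall survival will be estimated using the Kaplan-Meier method". It gives no censoring rule.

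Three sections govern what is observed after treatment:

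- **6.1 (schedule of events).** The last column is headed "Follow-up (q 56 days until 1 year". It is marked for history and physical examination, performance status, "Tumor Measurements by physical examination", CBC and metabolic panel.
- **6.3.6 (Visits 7-10).** The timing is "Every 56 days to one year (typically month 6, 8, 10, 12", but the content is different: "Follow-up will consist of survival contacts via medical record review, telephone call, or review of the Social Security Index". Patients are followed "until subsequent CLL therapy, death, or discontinuation of trial participation"; progression is not among the stop events.
- **5.9.** Patients are "followed for 1 year after removal from treatment or until disease progression, initiation of subsequent CLL therapy, or death", whichever comes first.

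**The concern.** Sections 6.1 and 6.3.6 describe the same visits and cannot both be followed. Under 6.1 the patient is examined and has a blood count. Under 6.3.6 a telephone call or a check of a death index is enough. The stop rules and the lengths differ as well.

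The progression criteria in 7.1 rest on node measurements, liver and spleen examination, or blood counts, apart from transformation, which needs histology. A survival contact supplies none of these. If 6.3.6 governs, deaths would be captured systematically, but progression after Visit 6 would be found only when routine care happened to record it, at times that vary between patients. Examinations missed for this reason cannot be recovered later. Durability of response has the same gap, because 7.1 requires a partial response to last at least two months.

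**Working it through.** **Inputs from the documents.** Treatment lasts 56 days (5.8). Visit 6 is 56 days after the last dose, with a window of 7 days either side (6.1, 6.3.5). Later visits are every 56 days (6.1, 6.3.6). Sample size is 15 to 21 (10.2). Dose delays and early stopping are ignored, so all days are nominal.

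**Reproducing the plan's visit labels.** The last dose is Day 56, so Visit 6 is 56 + 56 = Day 112 (Days 105-119 with the window). Visits 7-10 are 112 + 56k for k = 1 to 4, that is Days 168, 224, 280 and 336. Dividing by 28 gives 6, 8, 10 and 12. These are the months named in 6.3.6, counted in 28-day months from first dose.

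**Length.** Section 5.9 counts one year from removal: 56 + 365 = Day 421. Visit 10 falls 421 - 336 = 85 days short of that. One more 56-day visit, at 336 + 56 = Day 392, would fit inside it.

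**Last mandated assessment.** Visit 6 has an examination and hematology in both 6.1 and 6.3.5. After it, 6.1 continues both and 6.3.6 continues neither.

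**Effect on the PFS median.** The documents give no expected PFS, so the true medians below are assumptions. With exponential PFS and median m (1 month = 30.4375 days), the chance of an event by day T is q = 1 - 0.5^(T/m). With no other censoring, the Kaplan-Meier curve reaches 0.5 if at least 8 of 15 or 11 of 21 patients have an event, so the chance is P(Bin(n, q) ≥ 8 or 11).

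Example: for m = 6 months (182.6 days) and T = 112, q = 1 - 0.5^(112/182.6) = 0.346. The tail probability is 0.107 for n = 15 and 0.072 for n = 21.

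| True median (months) | q to Day 112 | Estimable, n = 15 / 21 | q to Day 336 | Estimable, n = 15 / 21 |
|---|---|---|---|---|
| 2 | 0.721 | 0.967 / 0.985 | 0.978 | >0.99 / >0.99 |
| 3 | 0.573 | 0.717 / 0.751 | 0.922 | >0.99 / >0.99 |
| 4 | 0.471 | 0.411 / 0.396 | 0.852 | >0.99 / >0.99 |
| 6 | 0.346 | 0.107 / 0.072 | 0.721 | 0.967 / 0.985 |
| 9 | 0.247 | 0.016 / 0.006 | 0.573 | 0.717 / 0.751 |
| 12 | 0.191 | 0.003 / 0.001 | 0.471 | 0.411 / 0.396 |

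The Day 112 columns represent 6.3.6 with no later event counted. The Day 336 columns represent 6.1 with every progression detected. The break-even is a true median of 112 days (112/30.4375 = 3.68 months), where the Day 112 chance is 50%.

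**Partial response.** Visit 5 falls 1 to 28 days after Day 56, that is Days 57-84. A response first documented there is 112 - 84 = 28 to 112 - 57 = 55 days old at Visit 6, short of two months. With the 7-day windows of both visits the range is 105 - 91 = 14 to 119 - 57 = 62 days. A response first seen at Cycle 2 Day 1 (Day 29) is 112 - 29 = 83 days old at Visit 6 and is not affected.

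**The case against.** The strongest reply is that the analysis is modest and hedged. Section 10.4 makes it conditional on follow-up, attaches no hypothesis or precision target, and places it in a dose-finding study. That stands, and it limits the importance of the point. It does not tell staff which visit content to follow.

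Four further points stand and limit what may be claimed.

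- **Rapid progression.** The population is relapsed or refractory with an indication for treatment. If the true median is 2 to 3 months, it would usually be estimable even from examinations ending at Day 112. A reader might infer that the planned median PFS is unsupported altogether; the documents do not show that.
- **Later events are not all lost.** PFS counts deaths, and 6.3.6 includes record review at a single center. The Day 112 figures are therefore a worst case.
- **The 6.1 comparison is idealized.** The nodal-growth criterion needs two determinations two weeks apart, which 56-day visits do not provide. New palpable nodes and lymphocyte counts would still register.
- **The length conflict is soft.** Section 6.3.6 says its months are typical, and 6.1 leaves the visit numbering open-ended.

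Two stronger readings are tempting. One is that the post-treatment cytopenia criterion, which counts only from three months after treatment, could be met at Visit 7 under 6.1 but never under 6.3.6. That criterion also requires a marrow biopsy showing clonal infiltrate, and 6.1 schedules marrow only at Visit 5 for a suspected complete response. It does not separate the two schedules. The other is that 5.9 makes overall survival badly biased. Overall survival is not a listed endpoint, and any size for such bias would rest entirely on rates that the documents do not give.

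**Conclusion.** The conflict is real and should be resolved, though it does not touch the primary DLT/MTD endpoint. Sections 6.1 and 6.3.6 give incompatible content for the same visits, and 5.9 differs from 6.3.6 on the stop event and the length. The consequence for PFS is conditional: it arises if 6.3.6 is followed. If 6.1 governs, PFS remains assessable.

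Under 6.3.6 the PFS estimate is weakened to a degree that depends on the unknown true median. On the worst-case assumptions above, the loss is negligible at 2 months. At 6 months the chance of an estimable median falls from 97-98% to 7-11%, and at 12 months from about 40% to 0.1-0.3%. These figures rest on exponential PFS, no dropout, and complete detection of events up to the cut-off day. The partial-response gap is firmer because it follows from the visit days, but it applies only to responses first documented at Visit 5, and visit windows can shorten or lengthen it.

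**What to change.** Reconcile 5.9, 6.1 and 6.3.6 into one follow-up rule with one time origin (first dose or removal) and one stop point. Within it:

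1. Make 6.3.6 match the examination, tumor measurement and CBC that 6.1 already schedules every 56 days, until progression.
2. In 10.4, censor PFS at the last adequate disease assessment and state how new CLL therapy before progression is handled. Both 5.9 and 6.3.6 end observation at new therapy, so the case will arise.
3. Confirm a partial response first seen at Visit 5 at the next scheduled examination and CBC at least two months later. Nominally that is Visit 7.
4. Either keep the vital-status contacts of 6.3.6 after progression, or delete overall survival from 10.4.

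The cost is mostly wording. The examinations are new only relative to 6.3.6: up to 4 per progression-free patient, at most 21 × 4 = 84, and fewer as patients progress. Keeping the length in 5.9 adds one visit, at Day 392. The change should be made before follow-up visits begin.
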